7.7.1.4. Grade 4 Laboratory Abnormality or Clinical Event

For a Grade 4 clinically significant laboratory abnormality or clinical event, confirmed by repeat testing, that is considered to be related to study drug, **the participant will be discontinued from study drug**. The participant should be managed according to local practice. The participant should be followed as clinically indicated until the laboratory abnormality returns to baseline or is otherwise explained, whichever occurs first. A clinically significant Grade 4 laboratory abnormality that is not confirmed by repeat testing should be managed according to the algorithm for the new toxicity grade.

Study drug may be continued without dose interruption for a clinically nonsignificant Grade 4 laboratory abnormality (eg, Grade 4 creatine kinase elevation after strenuous exercise or triglyceride elevation that is nonfasting or that can be medically managed) or a clinical event considered unrelated to study drug.

Treatment-emergent toxicities will be noted by the investigator and brought to the attention of the Gilead medical monitor, and the appropriate course of action will be discussed and decided. Whether or not considered treatment-related, all participants experiencing AEs must be monitored periodically until symptoms subside, any abnormal laboratory values have resolved or returned to baseline levels or they are considered irreversible, or until there is a satisfactory explanation for the changes observed.

Any questions regarding toxicity management should be directed to the Gilead medical monitor.

8. STATISTICAL CONSIDERATIONS

Details of the statistical methods will be provided in the statistical analysis plan (SAP), including any deviations from the original statistical analyses planned.

8.1. Analysis Objectives and Endpoints

Objectives and endpoints are listed in Section [2](#).

8.1.1. Secondary Endpoints

Additional information on the secondary endpoints listed in Section [2](#) is provided below.

- Time (days) to sustained alleviation of targeted COVID-19 symptoms by Day 35

This secondary efficacy endpoint will be assessed via the participant symptom assessment. Symptom alleviation is defined as follows: all targeted symptoms scored moderate or severe at baseline are scored as mild or none for at least 48 consecutive hours, and all targeted symptoms scored mild or none at baseline are scored as none for at least 48 consecutive hours; the first day of the 48 consecutive hours will be considered the symptom alleviation date. Details of the COVID-19 symptoms to be assessed are provided in Section [6.3.7](#).

8.2. Planned Analyses

8.2.1. Interim Analysis

Before the final analysis, interim analyses may be conducted and the analyses may be submitted to regulatory agencies to seek guidance for the overall clinical development program or to request extension of indication to include the applicable age/weight band(s).

8.2.1.1. Planned Internal Analysis

For the purpose of assessing the dosing regimen, interim analyses of relevant safety and PK data will be conducted by Gilead. Further details will be provided in the safety review team (SRT) charter.

8.2.1.2. Data Monitoring Committee Analysis

An external DMC will review the progress of the study and perform interim review(s) of safety and available PK data. The DMC membership, activities, and meeting schedule will be defined in a DMC charter.

8.2.2. Final Analysis

The final analysis will be performed after all participants have completed the study, outstanding data queries have been resolved or adjudicated as unresolvable, and the data have been cleaned and finalized.

8.3. Analysis Conventions

8.3.1. Analysis Sets

8.3.1.1. Efficacy

The primary analysis set for efficacy analyses is defined as the Full Analysis Set (FAS). This will include all participants who (1) are enrolled into the study and (2) have received at least 1 dose of study drug.

8.3.1.2. Safety

The primary analysis set for safety analyses is defined as the Safety Analysis Set. This will include all participants who (1) are enrolled into the study and (2) have received at least 1 dose of study drug.

All data collected during treatment plus 30 days will be included in the safety summaries.

8.3.1.3. Pharmacokinetics

The PK Analysis Set will include all participants who (1) are enrolled into the study, (2) have received at least 1 dose of study drug, and (3) have at least 1 nonmissing PK concentration datum reported by the PK laboratory for GS-441524.

8.3.1.4. Virology

The Virology Analysis Set will include all participants who (1) are enrolled into the study, (2) have at least 1 dose of study drug, and (3) have positive SARS-CoV-2 viral load at baseline.

8.3.2. Data Handling Conventions

Natural logarithm transformation for PK parameters will be applied for PK analysis.

For summary statistics, PK concentration values below the limit of quantitation will be treated as zero at predose and one-half of the lower limit of quantitation (LLOQ) for postdose time points.

Laboratory data that are continuous in nature but are less than the LLOQ or above the upper limit of quantitation, will be imputed to the value of the lower or upper limit plus or minus 1 significant digit, respectively (eg, if the result of a continuous laboratory test is < 20, a value of 19 will be assigned).

Missing data can have an impact upon the interpretation of the study data. In general, values for missing data will not be imputed. However, a missing pretreatment laboratory result would be treated as normal (ie, no toxicity grade) for the laboratory abnormality summary.

All available data for participants that do not complete the study will be included in data listings.

8.4. Demographic and Baseline Characteristics Analysis

Demographic and baseline measurements will be summarized using standard descriptive methods.

Demographic summaries will include sex, race/ethnicity, and age. Baseline data will include a summary of weight, height, and body mass index.

No formal statistical testing is planned.

8.5. Efficacy Analysis

For all efficacy analyses, the FAS will be used, unless specified otherwise. No formal statistical testing is planned.

8.5.1. Primary Analysis

There is no primary efficacy analysis for this study; all efficacy endpoints are either secondary or exploratory.

8.5.2. Secondary Analyses

The time to sustained alleviation of targeted COVID-19 symptoms by Day 35 is calculated as the symptom alleviation date minus the first dose date plus 1 day. In case, prior to data cutoff a participant:

- Completes the study without alleviation of targeted COVID-19 symptoms
- Discontinues from the study early prior to alleviation of targeted COVID-19 symptoms (due to AE, lack of efficacy, investigator's discretion, noncompliance with study drug, protocol violation, participant decision, lost to follow-up)

The time to sustained alleviation of targeted COVID-19 symptoms will be calculated as the last date on which the symptom alleviation is assessed by Day 35 minus the first dose date plus 1 day or Day 34, whichever occurs first.

In addition, if prior to data cutoff a participant:

- Dies from any cause prior to alleviation of targeted COVID-19 symptoms
- Takes rescue medication prior to alleviation of targeted COVID-19 symptoms

he/she will be regarded as not having the event of interest and will be censored at Day 34.

The timing to sustained alleviation of targeted COVID-19 symptoms will be estimated by cohort and overall using the Kaplan-Meier (KM) method. The median time to sustained alleviation of targeted COVID-19 symptoms along with the 95% CI will be presented. The proportion of participants with sustained alleviation of targeted COVID-19 symptoms using KM estimates will be provided in summary tables and plots by cohort and overall.

For continuous variables, data and change from baseline at all scheduled time points will be summarized by cohort and overall. For categorical variables, the number and percentage of participants in each category within a variable will be presented by cohort and overall.

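### Participants who leave for lack of efficacy get a time at their last symptom assessment while rescue users are held to Day 34, which biases the proportion alleviated upward

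*Protocol*

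**What the plan says.** Protocol section 8.5.2 sets two rules for participants who do not reach alleviation.

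- **Last-assessment rule.** This covers completers without alleviation and anyone who fits "Discontinues from the study early prior to alleviation of targeted COVID-19 symptoms (due to AE, lack of efficacy", along with several other reasons such as participant decision and loss to follow-up. Their time is "the last date on which the symptom alleviation is assessed by Day 35 minus the first dose date plus 1 day or Day 34", taking the earlier of the two. The text does not say whether this time is censored or an event.
- **Day 34 rule.** This covers a participant who "Dies from any cause prior to alleviation of targeted COVID-19 symptoms" or who "Takes rescue medication prior to alleviation of targeted COVID-19 symptoms". Such a participant "will be regarded as not having the event of interest and will be censored at Day 34".

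The endpoint "will be estimated by cohort and overall using the Kaplan-Meier (KM) method". Besides the median with its 95% CI, "The proportion of participants with sustained alleviation of targeted COVID-19 symptoms using KM estimates will be provided in summary tables and plots", for each cohort and for the whole study. The section gives no reason for treating a lack-of-efficacy leaver differently from a rescue user.

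**The concern.** Kaplan-Meier treats a participant censored at exit as exchangeable with those still under observation. That is hard to accept when the recorded reason for leaving is that the drug did not work. The Day 34 rule already treats rescue use as failure by keeping the participant in the risk set without an event. Someone who leaves for lack of efficacy without taking rescue medication has failed in a similar sense, but is removed and implicitly given the stayers' later recovery.

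The resulting bias is in the favourable direction. The study is single-arm (section 3.1), so no control curve carries the same bias. Cohorts 1-4 have 12 evaluable participants each (section 4.1), so one participant shows in a cohort curve. Section 8.2.1 allows interim analyses to be submitted to request an extension of the indication, so cohort-level descriptive results may be read by regulators.

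**Working it through.** The protocol states no dropout rate, alleviation rate or power for this endpoint, so there is no figure to reproduce. What follows shows direction and rough size under stated assumptions.

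**Inputs from the protocol:** the two rules and the Kaplan-Meier estimator (section 8.5.2); 12 evaluable per cohort in Cohorts 1-4 and at least 52 in total (section 4.1).

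**Assumptions:** leavers exit on Day 4 or Day 6 without alleviation; 1 of 12 (or 5 of 52) other participants never alleviate; the rest alleviate on a log-normal pattern with median 8 days. Last-assessment times are read as censored.

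**Step 1: the two rules on the same data.** Let n be the number of participants, k the leavers, j the others who never alleviate, and a the alleviations up to the exit day.

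- Leavers censored at exit: proportion = 1 - [(n - a)/n] x [j/(n - a - k)]
- Leavers held to Day 34: proportion = (n - k - j)/n

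For n = 12 and j = 1, the assumed pattern gives a = 1 by Day 4 and a = 3 by Day 6.

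- k = 1: 1 - (11/12)(1/10) = 0.908 or 1 - (9/12)(1/8) = 0.906, against 10/12 = 0.833. Gap about 7 points.
- k = 2: 1 - (11/12)(1/9) = 0.898 or 1 - (9/12)(1/7) = 0.893, against 9/12 = 0.75. Gap 14 to 15 points.

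For n = 52 and j = 5, with exit on Day 4: k = 3 gives 0.897 against 0.846; k = 5 gives 0.892 against 0.808; k = 10 gives 0.878 against 0.712.

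**Step 2: a second model.** This used 2,000 simulated cohorts per setting, exponential alleviation with median 7 days, and exits on Days 4-8. For n = 12 at Day 33:

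- 1 leaver: 0.959 against 0.881 (8 points)
- 2 leavers: 0.957 against 0.802 (about 15 points)

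**Step 3: where the gap comes from.** The held figure is nearly the other figure times the share who stayed: 0.959 x 11/12 = 0.88 and 0.957 x 10/12 = 0.80. The whole gap therefore reflects giving leavers no alleviation at all after exit.

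**Step 4: allow leavers to recover.** Take the second model with 2 leavers of 12 and exit on Day 6. The stayers' rate is ln 2 / 7 = 0.099 per day, and 27 days remain to Day 33.

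- Leavers at half that rate: 1 - exp(-0.0495 x 27) = 0.74. True proportion = (10 x 0.957 + 2 x 0.74)/12 = 0.92. Censoring at exit is 4 points high; holding to Day 34 is 12 points low.
- Leavers at a quarter of that rate: 1 - exp(-0.0248 x 27) = 0.49. True proportion = (10 x 0.957 + 2 x 0.49)/12 = 0.88. Each rule misses by about 8 points, in opposite directions.

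**Step 5: the median.** Across the Step 1 scenarios, with up to 3 leavers of 12 or 10 of 52, the median is 0 to 2 days shorter under the last-assessment rule. With 1 or 2 leavers of 12 it does not move.

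**Step 6: the unstated status of the times.** If the last-assessment times were read as events, 5 leavers of 52 would give 47/52 = 0.904, compared with 0.892 if censored and 0.808 if held to Day 34. The direction is the same and the inflation larger.

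**The case against.** Death rules out later alleviation and rescue medication confounds it, whereas leaving the study produces missing follow-up. Using different rules for these is coherent, and holding leavers to Day 34 is a choice of estimand that counts leaving as failure. This largely stands. Step 4 shows that, as an estimate of actual recovery, the held figure misses by more than the censored one unless leavers recover at below roughly a quarter of the stayers' rate. Section 1.1 cites a median illness of 5 to 7 days in school-aged children, so some recovery after exit is likely, although that population was not selected for high risk.

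Few participants may be affected. Dosing lasts 5 days (section 3.2). Section 3.3.1.2 lists only withdrawal of consent or assent and death as reasons for discontinuing the study. Section 6.4.1 asks sites to keep participants who stop drug in follow-up, and stopping drug alone does not trigger the rule. A leaver who took rescue medication first also meets the Day 34 rule, though the section does not say which rule prevails. These points limit the size but do not remove the issue, because section 8.5.2 itself names lack of efficacy as a reason for leaving.

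A reader might infer that adverse-event leavers are failures too. The documents do not support that: leaving for an adverse event says nothing direct about COVID-19 symptom resolution. A reader might also infer that the curve will be inflated by 15 points. That figure rests on an assumed 2 of 12 leaving and on none of them recovering.

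**Conclusion.** The point holds for participants who leave for lack of efficacy. Giving them a last-assessment time, read as censored, biases the Kaplan-Meier proportion alleviated upward whenever they recover more slowly than those who stay. It also sits awkwardly beside the plan's treatment of rescue use as failure. Under the assumptions shown, the two rules differ by about 8 points with 1 such leaver in a cohort of 12 and about 15 points with 2. The true proportion lies between them if leavers recover at some rate between zero and that of the stayers. The median is little affected.

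The documents do not support calling the rule an outright contradiction or saying that it undermines the trial's conclusions. The endpoint is secondary, no formal testing is planned (sections 8.5 and 8.5.1), and the primary endpoints are PK and safety (section 2). This is a cheap improvement with limited impact.

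**What to change.** In section 8.5.2:

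1. Move study discontinuation for lack of efficacy before alleviation into the Day 34 list, stating that it is counted as failure in the same way as rescue use.
2. Keep the last-assessment time for the other reasons, and state that these times are censored.
3. Report the proportion alleviated under both rules as bounds, by cohort and overall.
4. Include a sensitivity analysis that also holds adverse-event leavers to Day 34.

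The cost is a sentence or two of text and a few extra table rows. No visit, sample size or data collection changes. The downside is a slightly less favourable main curve that may understate eventual alleviation, which is why both figures should be shown.

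### Section 8.5.2 censors deaths and rescue users at Day 34 with no cap at the data cutoff, so a symptom curve drawn during follow-up would read slightly low

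*Protocol*

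**What the plan says.** Protocol section 8.5.2 gives two rule sets for children without alleviation, and both refer to a data cutoff.

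- The first opens "In case, prior to data cutoff a participant" and covers children who complete the study, or leave it early, without alleviation. Their time is the last assessment date "minus the first dose date plus 1 day or Day 34, whichever occurs first".
- The second opens "In addition, if prior to data cutoff a participant" and covers death from any cause and rescue medication before alleviation. For these, "he/she will be regarded as not having the event of interest and will be censored at Day 34". No earlier limit is given.

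The time to alleviation "will be estimated by cohort and overall using the Kaplan-Meier (KM) method".

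On timing, section 8.2.1 says: "Before the final analysis, interim analyses may be conducted and the analyses may be submitted to regulatory agencies". One stated purpose is an extension of indication for particular age or weight bands. The content of such an analysis is not restricted there. The two interim reviews whose content is described, in sections 8.2.1.1 and 8.2.1.2, cover safety and PK. The final analysis (section 8.2.2) follows completion of the study by all participants.

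**The concern.** Placing deaths and rescue users at the end of the observation window is a recognised way to keep them in the denominator as failures. It works because, with complete follow-up, everyone else could also have been observed to Day 34. At a cutoff taken while children are in follow-up, that symmetry is lost. A rescue user first dosed 6 days before the cutoff stays at risk for 34 − 6 = 28 days that have not happened. A child dosed on the same day who is simply not yet better can contribute at most 6 days. The later risk sets then hold too many children who cannot have the event, and the curve is pulled down.

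At stake is a symptom curve that might accompany an early submission. Part of its level would reflect how recently children were enrolled. Cohorts open in a staggered manner and curves are produced overall as well as by cohort, so an overall curve could mix a finished cohort with one still in follow-up.

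**Working it through.** The plan states no numerical figure for this rule, so there is none to reproduce. The check has two parts: the direction, which needs no assumed rates, and the size, which does.

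**Direction.** The Kaplan-Meier proportion alleviated by day t is 1 − Π(1 − d_s / n_s) over days s ≤ t, where d_s is the number alleviated on day s and n_s the number at risk. Write n_s = o_s + h_s. Here o_s counts children observed to day s who have had neither alleviation nor a prior death or rescue, and h_s counts death or rescue cases held in the risk set.

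- As written, h_s includes every death or rescue case before the cutoff, up to s = 34.
- With a cap at the cutoff, h_s includes only those whose possible follow-up at the cutoff reaches day s.

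The d_s and o_s are the same under both rules, and h_s as written is never smaller. Each d_s / n_s is therefore never larger, and the proportion alleviated can only be equal or lower. The two rules coincide when every included child has possible follow-up to Day 34.

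**Size: inputs.** From the Protocol: Day 34 as the limit, the Kaplan-Meier estimator, and 12 evaluable participants in each of Cohorts 1 to 4 (4 × 12 = 48). Assumed, because the Protocol gives no values:

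- exponential alleviation times rounded up to whole days, with a median of 7 days (section 1.1 cites median illness durations of 5 and 7 days by age group);
- 5%, 10% or 20% of children assigned a death or rescue day between Days 2 and 8, which counts only if it precedes alleviation;
- uniform accrual, with the cutoff at the end of accrual;
- children still in follow-up without alleviation censored at the cutoff.

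**Size: simulated mean proportion alleviated by Day 28, 48 children**

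| Accrual | Death/rescue | Full follow-up | As written | Loss (points) | Capped at cutoff |
|---|---|---|---|---|---|
| 60 days | 5% | 91.1% | 90.2% | 0.9 | 91.2% |
| 60 days | 10% | 87.9% | 86.1% | 1.8 | 87.8% |
| 60 days | 20% | 82.4% | 79.8% | 2.6 | 82.3% |
| 180 days | 5% | 90.9% | 90.7% | 0.2 | 90.9% |
| 180 days | 10% | 88.2% | 87.7% | 0.5 | 88.2% |
| 180 days | 20% | 82.5% | 81.8% | 0.7 | 82.5% |

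The estimated median was 8 days in every one of these rows under the written rule, as with full follow-up.

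**Checks.**

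- With no death or rescue, the written and capped rules give the same value (93.9% at Day 28 with 60-day accrual).
- With 40-day accrual and a large sample, the Day 28 loss at a 7-day median is 90.9 − 88.9 = 2.0, 87.9 − 84.7 = 3.2 and 82.6 − 78.2 = 4.4 points at 5%, 10% and 20%. The largest loss across medians of 5, 7 and 10 days is 73.9 − 68.9 = 5.0 points (10-day median, 20%).
- When the cutoff falls after the last child has completed follow-up (12 children, 10% death or rescue), all variants give 88.2% at Day 28.

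**The case against.** The strongest reply is that the affected analysis may never be done. No interim symptom analysis is named, the described interims concern safety and PK, and the final analysis has no child still in follow-up. An interim on a weight band that has finished follow-up is also unaffected. The Day 34 rule is deliberate and correct with complete data. The loss is small against sampling error: the binomial standard error of an 80% proportion is √(0.8 × 0.2 / 12) = 11.5 points for 12 children and √(0.8 × 0.2 / 48) = 5.8 points for 48. All of this stands and limits the severity.

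Two things remain. Section 8.2.1 does not confine its interim analyses to safety and PK, and the rule in 8.5.2 is itself written around a data cutoff. Nor is this a silence for the SAP to fill, since a cap there would depart from a time the Protocol states.

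A reader might infer more, but the Protocol does not support it:

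- *That children still in follow-up without alleviation would be dropped, which would bias the curve upward.* They fit none of the listed categories; for instance, they are not children of whom it can be said "Completes the study without alleviation of targeted COVID-19 symptoms". But efficacy uses the Full Analysis Set, which contains every enrolled and dosed child, and censoring at last assessment is the ordinary convention that a SAP commonly states. The general statement that "In general, values for missing data will not be imputed" does not imply dropping, because right-censoring is not imputation.
- *That unalleviated completers and leavers would count as events, because their sentence lacks the word censored.* The group is defined as not having alleviated, so this is a matter of drafting.
- *That the distortion is large.* A fall from 80% to 73% by Day 34 can be produced, but only by assuming 20% rescue and all accrual within the 30 days before the cutoff. The Protocol gives neither figure, and staggered cohorts make so short a window hard to credit.

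**Conclusion.** The point holds in a limited form and is minor. As written, the rule keeps known non-events at risk beyond the follow-up that the cutoff allows, and this can only lower the Kaplan-Meier proportion alleviated. It matters only if section 8.5.2 is applied at an interim while some children are in follow-up and some have died or taken rescue. At a 7-day median and 5% to 20% death or rescue, the Day 28 loss is about 1 to 3 points with 60-day accrual, under 1 point with 180-day accrual, and up to 5 points in the most extreme 40-day setting tried. The rates, accrual pattern and alleviation distribution are assumptions; the direction is not. It would be wrong to conclude that a planned analysis is distorted, or that the final result is. The endpoint is secondary and descriptive, with no formal test, so no decision rule in the Protocol turns on it.

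**What to change.** In the death and rescue sentence of section 8.5.2, extend the censoring time to read: *Day 34 or the study day of the data cutoff, whichever is earlier*. In the simulations this cap recovers the full-follow-up value within simulation error. An equivalent choice is to restrict any interim symptom curve to children first dosed at least 34 days before the cutoff.

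For clarity only, the same paragraph can add that unalleviated children who complete, leave or are still in follow-up at the cutoff are censored at their last symptom assessment, keeping the existing Day 34 limit.

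The cost is a sentence or two of wording, with no added participants, visits or data. An interim estimate would use slightly less follow-up time. The final analysis would not change.
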